4.2. Scientific Rationale for Study Design

This study is a combination of a Phase 1, FIH, dose escalation study and a Phase 2, dose expansion study. Subjects to be treated in the study are those with advanced cancers, and a control group is not deemed appropriate.

In this study, the effects of desialylation of immune and tumor cells on the antitumor immunity will be explored, with E-602 given as a monotherapy and together with a PD1-pathway inhibitor. The tumor types chosen to be studied are populations enriched for patients with tumors that have greater amounts of sialoglycan modifications with immunoinhibitory potential, such as melanoma (Prendergast 2021), lung, colon, pancreatic, ovarian, breast, gastric/EGJ, head and neck and urothelial cancers (data on file).

In Phase 1 of the study, dose escalation (5 dose levels planned) will follow a modified 3+3 design for the E-602 monotherapy, and dose escalation (2 dose levels) for the combination therapy with cemiplimab will be carried out after the same dose level in monotherapy has been deemed tolerable. This design will assure protection of subject safety while identifying an MTD and an appropriate dose for dose expansion in Phase 2. Phase 1 cohorts can be backfilled at the judgement of the Sponsor in a dose cohort as needed to obtain additional safety, PK, and pharmacodynamic data at a particular dose level.

The RP2D(s) for monotherapy and combination therapy will be selected separately based on the totality of data including safety, pharmacodynamic, and PK data collected during Phase 1.

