6.1 General Statistical Considerations

In general, all analyses will be summarized by dose level and study treatment (e.g. monotherapy, combination with cemiplimab). Safety analysis will be based on the safety analysis population. The primary efficacy analysis will be based on the efficacy evaluable population by study treatment and/or tumor indication.

For each tumor indication, subjects administered the same study treatment may be combined for analysis purposes, regardless of study phase. Statistical inference, when performed, will be assessed at the 2-sided nominal 5% significance level without multiplicity adjustment. Point estimates will be accompanied by 95% confidence intervals (CIs). For the ORR endpoint assessed per the Simon's 2-stage design, the 2-sided 80% CI may be used.

For continuous variables, the number of observations (n), mean, standard deviation, median, minimum, and maximum will be provided as summary statistics. The mean and median will be reported to one additional decimal place compared to the original data. The standard deviation will be reported to two additional decimal places compared to the original data and the minimum and maximum will be reported to the same number of decimal places as the original data.

For categorical variables, the frequency and percentage in each category will be displayed. Percentages (e.g., for AEs and concomitant medications) will be calculated out of the population total for each cohort. Footnotes will clarify the denominator used in each output if other than the analysis set stated in the title. Percentages will be reported to one decimal place throughout unless the percentage is 100 (in which case no decimal places will be presented) or if the frequency count is zero (in which case no percentage will be presented).

For time to event data, unless otherwise noted, the median value, 25th percentile and 75th percentile will be calculated using the Kaplan-Meier method. The Brookmeyer and Crowley method will be used to calculate the CI of the median value (Brookmeyer and Crowley 1982). Also, the Greenwood formula will be used to calculate the CI of the rate of interest pertaining to the time to event data, at a given time point estimated using the Kaplan-Meier method (Kalbfleisch and Prentice 2002). The time to event analysis will be calculated only if an adequate number of responses are observed to warrant.

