6.8.1.1 Pharmacodynamic Biomarker Definitions

Baseline

For the purposes of the pharmacodynamic biomarker analyses, baseline will be defined as indicated for each parameter:

- Chemokine Panel, Pro-inflammatory Panel, and C3a: last non-missing measurement prior to the first administration of E-602 treatment.
- Immunophenotyping parameters: Average of non-missing measurements prior to the first administration of E-602 treatment or the only available measurement prior to the first administration of E-602 should only one measurement be available.
- IHC: last non-missing measurement prior to the first administration of E-602 treatment.

Fold-change from Baseline

Fold-change from baseline is the ratio of the post-baseline value over the baseline value.

Fold-change from Baseline = Post-baseline Value/Baseline Value.

*Note: "value" in MFI of PNA = MFI (timepoint) - MFI (FMO)

Data Handling and Exclusions

The following quality metrics will be used to exclude entire visit/timepoint results from the analysis. Any visit/timepoint meeting the exclusion criteria will be noted in the listing of the corresponding Biomarker Panel.

Biomarker Panel	Exclusion Criteria
Immunophenotyping (FACS)	<65% live cells by Cellometer count OR Received for PBMC processing >72 hours after collection
Tissue IHC	H&E Adequacy = "N"

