6.8.1.2 Pharmacodynamic Biomarker Analysis

Immunophenotyping (FACS), Chemokine Panel, Pro-inflammatory Panel and C3a biomarkers will be summarized using descriptive statistics for select parameters including absolute measurements and fold change from baseline by visit. Tissue IHC biomarkers will be summarized using descriptive statistics for select parameters including absolute measurements and change from baseline.

Sensitivity pharmacodynamic biomarker analyses may also be performed. For Tissue IHC biomarkers, data may be summarized for the patients for which there are matched pre- and on-treatment and the on-treatment biopsy was collected within 48 hours after the last dose of E-602. All biomarker results will be presented in a by-subject listing.

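### Biomarker fold-change is a raw ratio with an arithmetic mean among its summaries and no rule for a net PNA MFI baseline at or below zero; a geometric mean ratio and a prespecified floor rule would be better

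*SAP*

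**What the plan says.** SAP 6.8.1.1 defines "Fold-change from Baseline = Post-baseline Value/Baseline Value", with no log transform. For one parameter it adds that the value "in MFI of PNA = MFI (timepoint) - MFI (FMO"), so background is subtracted at every time point, in both numerator and denominator.

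Baselines differ by panel. For FACS the rule is "Immunophenotyping parameters: Average of non-missing measurements prior to the first administration of E-602 treatment"; for the soluble markers it is "Chemokine Panel, Pro-inflammatory Panel, and C3a: last non-missing measurement prior to the first administration of E-602 treatment". The footnotes to Protocol Tables 4 and 5 plan two pre-dose samples on Cycle 1 Day 1 for both groups of markers.

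SAP 6.8.1.2 summarises these markers by "absolute measurements and fold change from baseline by visit" and lists all results by subject. Under SAP 6.1, "the number of observations (n), mean, standard deviation, median, minimum, and maximum will be provided"; Protocol 9.2.1 adds quartiles. Neither document names a geometric mean. The FACS exclusions in SAP 6.8.1.1 concern cell viability and sample age only. Tissue IHC is summarised as arithmetic change, so this point does not touch it.

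Protocol 4.2 selects the RP2D "based on the totality of data including safety, pharmacodynamic, and PK data collected during Phase 1".

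**The concern.** The arithmetic mean is a poor summary of a ratio. A chance-low baseline inflates the ratio by more than an equally chance-high baseline deflates it, so the average exceeds 1 when nothing has changed. For the soluble markers this would read as a rise in cytokines or C3a, although Protocol 2.1 expects no cytokine activation.

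For PNA MFI there is a second problem. Subtracting FMO shrinks the denominator, and a net baseline close to or below zero gives a very large or sign-reversed ratio. Dose cohorts hold 3 to 6 subjects, or at most 15 with backfill, so one such ratio can dominate the mean. Protocol 4.3.1 treats immune desialylation as a critical indicator of activity, and Protocol 4.1.1 allows escalation to stop before the MTD partly on pharmacodynamic data. The summary should therefore be sound even though the endpoint is exploratory.

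**Working it through.** The documents give no fold-change figure, assay CV or FMO share, so there is no stated number to reproduce. What can be computed is how the planned summaries behave with no drug effect, over a range of assumptions.

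**1. Single baseline (chemokines, pro-inflammatory panel, C3a).** Let post value Y and baseline X be independent lognormal with the same median and log-scale SD s. Then log(Y/X) is normal with mean 0 and variance 2s², so E[Y/X] = exp(2s²/2) = exp(s²). Since CV² = exp(s²) - 1, this equals 1 + CV².

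- s = 0.3: exp(0.09) = 1.09
- s = 0.4: exp(0.16) = 1.17
- s = 0.6: exp(0.36) = 1.43
- CV 20%: 1 + 0.04 = 1.04; CV 10%: 1.01

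**2. Averaged two-sample baseline (FACS), no background.** The denominator is (X1 + X2)/2. By simulation, at least 1,000,000 draws per row:

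| s | Mean ratio, single baseline | Mean ratio, two-sample average | Geometric mean and median, two-sample average |
|---|---|---|---|
| 0.3 | 1.09 | 1.05 | 0.98 |
| 0.4 | 1.17 | 1.09 | 0.96 |
| 0.6 | 1.43 | 1.21 | 0.92 |

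Averaging about halves the upward bias; at CV 20% the mean is 1.02. The last column matters for the remedy. An arithmetic baseline average exceeds the geometric one, so even the geometric mean and the median fall below 1. If the two pre-dose values are averaged as logs, log Y - (log X1 + log X2)/2 has mean 0 and the geometric mean ratio is 1.00 at every s.

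**3. Background-subtracted PNA MFI, two-sample average.** Assumptions, none from the documents: raw MFI lognormal with the CV shown, FMO as the stated share of mean raw MFI, and FMO noise CV 5%. A denominator that can cross zero gives a ratio with no finite expectation, so the table shows the spread of the 15-subject cohort mean.

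| FMO share | Raw CV | Net baseline ≤ 0 | Cohort mean, 5th to 95th percentile | Cohort mean above 1 |
|---|---|---|---|---|
| 25% | 20% | 0.0% | 0.90 to 1.19 | 65% |
| 50% | 20% | 0.0% | 0.86 to 1.37 | 72% |
| 50% | 30% | 0.1% | 0.81 to 1.93 | 79% |
| 70% | 30% | 5.7% | -3.8 to 6.4 | 59% |
| 80% | 30% | 17% | -7.1 to 8.8 | 42% |

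At 70% and 30%, the chance that a 15-subject cohort has at least one non-positive net baseline is 1 - (1 - 0.057)^15, about 0.59, and the cohort mean is negative in 17% of cohorts. The median ratio in that setting is 0.79, so it too moves once non-positive baselines are common.

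**The case against.** The strongest reply is that the plan does not rest on the mean. Median, minimum, maximum, quartiles and absolute values by visit are also planned, with a by-subject listing, so a single wild ratio would be visible. The endpoints are exploratory and descriptive, with no test or threshold. At a CV of 20% or less without background, the bias is at most 4%, or 2% for FACS, whose averaged baseline already reduces it. All of this stands, and it limits the weight of the point.

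It does not remove the point. The SAP does not say which summary leads, and the mean is a planned one. Nor do any of these summaries tell the programmer what to do with a net PNA MFI at or below zero.

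A reader might infer three stronger things that the documents do not support.

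- That the mean fold-change always drifts upward. For PNA MFI near background it is unstable in either direction.
- That FMO subtraction affects every MFI parameter or the baseline alone. It is stated only for PNA, at all time points.
- That a biased mean would reorder the doses or set the RP2D. No section makes mean fold-change a criterion. A similar bias at each dose would leave the order unchanged; reordering would need near-zero net baselines, which are possible but not shown.

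**Conclusion.** The point holds in limited form. The planned arithmetic mean of raw ratios has a null expectation above 1: about 1.09 to 1.43 for single-baseline panels and 1.05 to 1.21 for FACS without background, at assumed log-scale SDs of 0.3 to 0.6. It is negligible to small when assay CV is low. The more consequential gap is the missing rule for non-positive net PNA MFI. It matters only if background is a large share of signal, where a 15-subject mean can range from about -4 to 6 under no effect.

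The size rests wholly on assumed CVs and FMO shares; the sponsor's assay data would settle it. This is a minor-to-moderate exploratory reporting point. It does not affect the ORR analysis, the two-stage design or the sample size.

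**What to change.** In SAP 6.8.1.1 and 6.8.1.2:

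- Analyse log(post/baseline) and make the geometric mean ratio with its 95% CI the lead summary for FACS, chemokine, pro-inflammatory and C3a markers, with the planned median beside it.
- Average the FACS pre-dose values on the log scale; otherwise the geometric mean ratio falls below 1 under no effect.
- Prespecify what happens when net PNA MFI is at or below an assay floor: either set it to the floor and flag it, or analyse on the difference scale. Apply the rule to each sample, pre- and post-dose, before logs or averages are taken, since a log ratio is undefined at or below zero.
- Show change in net MFI alongside the ratio, and report how many values were floored.

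The cost is SAP wording and minor programming, with no new data. The floor must be chosen in advance from assay performance, and floored subjects' ratios will depend on it. In cohorts of 3 to 6 the confidence intervals will be wide.

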6.8.1.2 Pharmacodynamic Biomarker Analysis

Immunophenotyping (FACS), Chemokine Panel, Pro-inflammatory Panel and C3a biomarkers will be summarized using descriptive statistics for select parameters including absolute measurements and fold change from baseline by visit. Tissue IHC biomarkers will be summarized using descriptive statistics for select parameters including absolute measurements and change from baseline.

Sensitivity pharmacodynamic biomarker analyses may also be performed. For Tissue IHC biomarkers, data may be summarized for the patients for which there are matched pre- and on-treatment and the on-treatment biopsy was collected within 48 hours after the last dose of E-602. All biomarker results will be presented in a by-subject listing.

6.8.2 Exploratory Efficacy Analyses Based on iRECIST

If an adequate number of responses are observed to warrant, additional efficacy endpoints such as iORR, iDoR, iPFS based on iRECIST criteria may be analyzed similarly as their counterparts defined based on the RECIST criteria. For the iORR endpoint, iCR and iPR after iUPD will be included. For iDoR and iPFS, the event will be iCPD (confirmed PD) or death, whichever is earlier.

7 INTERIM ANALYSIS

7.1 Phase 1

An SDRC, consisting of the principal investigators and members of the Sponsor, will review safety data on an ongoing basis and after at least 3 subjects have completed the DLT-assessment period during dose escalation for a dose cohort. The committee will make dose de-escalation/escalation recommendations based on accumulating data. Details of the committee structure and meetings are described in the SDRC charter.

7.2 Phase 2

In addition to the ongoing review of safety data, the SDRC will also review the efficacy data at the end of Stage 1 per the Simon's 2-stage design. For the expansion cohort in Phase 2, efficacy data including but not limited to the number of subjects who achieved objective response and duration of response will be reviewed by the SDRC to determine if criteria to proceed to Stage 2 are met.

Additional interim analyses not planned as a part of the study design may also be performed and documented.

8 CHANGES FROM PROTOCOL-SPECIFIED ANALYSIS

There are no changes from the analysis specified in protocol v8.0.

